Primary efficacy parameter: Live birth rate

Secondary efficacy parameters: Singleton live birth rate, ovulation rate, cycles to first ovulation, cycles to conception (defined by positive serum HCG), abortion rate, cycles to pregnancy (defined by detection of fetal heart beat), and weeks from pregnancy to live birth.

NICHD Reproductive Medicine Network
PPCOS-Pregnancy in Polycystic Ovary Syndrome Protocol
Statistical Analysis: The primary analysis will use an intent-to-treat approach to

examine differences in the live birth rate among three treatment arms. A chi-square test will be used to compare the proportion of live births between the combined clomiphene citrate/Metformin XR group versus the group of either Metformin XR alone or clomiphene citrate alone that has the higher proportion of live births. If this comparison is not significant a chi-square test will be used to compare the proportion of live births between the Metformin XR alone versus clomiphene citrate alone. Logistic regression models will be used in secondary (or supplemental) analyses to evaluate the predictive value of treatment condition, clinical site, prior exposure to either clomiphene citrate or metformin XR, body mass index, and other explanatory variables on binary outcomes (e.g., , abortion, ovulation). Cox proportional hazards models and a Kaplan-Meier method will be applied to compare time to event (eg. Cycles to first ovulation, cycles to pregnancy) between the treatment groups. An interim analysis, incorporating an O'Brien-Fleming adjustment, will be performed when half of the study participants have completed treatment.

Anticipated time to completion: A total of three to four years will be required to complete the study; two year enrollment period, 30 week treatment period, with one year additional observation to determine pregnancy outcomes. This will be accomplished by enrolling 50-90 PCOS women per center over the two-year enrollment period. There are 12 centers currently participating. Other centers may be added.

II. BACKGROUND

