.50	.35	206/arm	237/arm	711
.45	.30	197/arm	226/arm	678
.40	.25	185/arm	213/arm	639
.35	.20	168/arm	193/arm	579

Based on these results, it is concluded that a study with 226 patients/arm is adequately powered to detect an absolute difference of 15% in live birth rates between two treatment arms, given the best estimates of success rates from the available literature.

A continuity correction was not applied to the sample size estimates for the chi-square test statistic. Such a correction is not necessary due to the expected size within each cell (32).

NICHD Reproductive Medicine Network
 PPCOS-Pregnancy in Polycystic Ovary Syndrome Protocol

6. Total Sample Size

The study will include 678 patients (226 per treatment arm).

C. Allocation of Intervention

1. Timing

A timeline is provided below:

Figure 1: Study Overview

Time line (~weeks)	-4 to 0	1	1-30	~~30-70
Study Phase	Consent PCOS Screen	Progestin withdrawal and Randomization		Pregnancy
Treatments	None- Complete infertility evaluation as necessary	Treatment Arm 1	Metformin XR	None-Collect pregnancy outcome data
		Treatment Arm 2	Clomiphene citrate	
		Treatment Arm 3	Metformin XR/Clomiphene citrate	
Visits	1 or more visits	2-30 (maximum weekly visits for 6 ovulatory cycles)		As necessary

2. Method

a. Randomization Scheme

Six hundred seventy-eight (678) women will be randomized to one of the three treatment conditions. Using a 1:1:1 treatment ratio, there will be 226 women assigned to each treatment arm. The scheme will be a stratified randomization with permuted blocking within each stratum. Stratification variables will be site and prior exposure to either

NICHD Reproductive Medicine Network
PPCOS-Pregnancy in Polycystic Ovary Syndrome Protocol
clomiphene citrate or metformin XR. The DCC statistician will generate the randomization scheme for the study. Because this is double-blind study, the randomization scheme (including block size) will not be disclosed to the RMN investigators or staff, including the Lead Investigators. Unless otherwise specified, treatment arm data will be presented in a blinded fashion within DSMB reports.

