The completed case report forms (CRF) will follow these guidelines: All data on the CRFs will be entered in ink. No data entry in the original CRF may be deleted or corrected by erasure, use of ink eradication fluid or any other such means. When a data entry is in error, draw a single line through the erroneous entry (the original data must remain discernible) and indicate the correct data in whatever way is appropriate. These changes should be initialed by the P.I. or designated study coordinator. Validity of data

NICHD Reproductive Medicine Network
PPCOS-Pregnancy in Polycystic Ovary Syndrome Protocol
recorded on CRFs during each patient visit will be attested to by one of the investigators
by a dated signature on an appropriate CRF page. All questions should be answered.
Data management will be as per DCC guidelines.

R. Competency to perform procedure/tests in the protocol

The principal investigator will be responsible for ensuring that laboratory and patient tests performed as part of the study are performed by competent personnel. These tests include semen analysis, ultrasonography of the pelvis, sonohysterography and/or hysterosalpingography of the uterus and fallopian tubes. The criteria for determination of competency may vary between sites in the study.

V. DATA ANALYSIS

All statistical tests will test non-directional hypotheses. The level of significance will be set at 0.05 for primary analyses and 0.05 for secondary analysis. An intent-to-treat principle will be employed during the primary analysis of the primary efficacy and safety measures. For the intent-to-treat analyses, randomized women will be included regardless of whether or not the patient received the assigned treatment, the patient was compliant with the treatment plan, and/or the treatment was administered according to randomization assignment.

A. Primary Efficacy Measure

Primary Analysis: A live birth will be defined as delivery of any viable infant. The primary analysis of the primary endpoint will include the following procedures. A chi-square test for equal proportions will be performed to evaluate whether live birth rate in Metformin/clomiphene group is the same as one in the group of either Metformin alone or clomiphene alone that has the higher live birth rate. If the test is not significant, a standard chi-square test will be used to examine differences in proportions in live births

NICHD Reproductive Medicine Network

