PPCOS-Pregnancy in Polycystic Ovary Syndrome Protocol
between the groups of Metformin alone and clomiphene alone. The level of significance for all tests included in the primary analysis will be 0.05.

Supplemental analyses: A set of secondary (supplemental/sensitivity) analyses of the primary endpoint will be conducted after the primary analysis has been performed using the intent-to-treat approach. All secondary analyses of the primary endpoint will be considered exploratory since the study has not been adequately powered for this set of supplemental analyses. Due to the exploratory nature of these analyses, the level of significance for the secondary analyses will be set at 0.05 (two-tailed) to reduce the Type II error rate.

Initially, a comparison of the internal consistency of live birth rates across sites will be examined using logistic regression analysis. Sites with similar live birth rates may be collapsed. For the regression model, the data will be examined to determine whether there is a site by treatment interaction effect. The recommended significance level is an alpha of 0.10 since the power to detect interactions is low. In the event that there is a significant interaction term, clinical site will be included as a covariate in all subsequent secondary analyses.

Next, logistic regression models will be used to evaluate the predictive value of treatment condition, clinical sites (if needed), prior exposure to either clomiphene citrate or metformin XR, and other explanatory factors on live birth rate. Examples of potential explanatory variables include: age, prior parity, body mass index, waist hip ratio, baseline proinsulin, insulin, and glucose values, and baseline testosterone values. In addition, we will examine to what extent change in baseline values is related to live birth rate.

Supplemental sensitivity analysis will also include an analysis of 'evaluable only' patients only (e.g., excluding randomized patients who were deemed to be ineligible later RMN Protocol
08Jan2004

NICHD Reproductive Medicine Network
PPCOS-Pregnancy in Polycystic Ovary Syndrome Protocol
or excluding patients who did not adhere to medication regimen) according to the
protocol).

B. Safety Measures

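### The primary chi-square ignores the factors used to stratify randomisation, and site enters the exploratory models by the wrong rule: a small, free improvement, not a validity problem

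*Protocol*

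**What the plan says.** Protocol Section IV.C.2.a describes the allocation: "The scheme will be a stratified randomization with permuted blocking within each stratum". It continues: "Stratification variables will be site and prior exposure to either" clomiphene citrate or metformin XR. The synopsis states "There are 12 centers currently participating", so there are 12 × 2 = 24 strata.

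Section V.A fixes the primary test without those factors: "A chi-square test for equal proportions will be performed to evaluate whether live birth rate in Metformin/clomiphene group" is the same as in the better single-agent arm. If that test is not significant, a standard chi-square compares the two single agents. The synopsis says the same.

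For the exploratory logistic models of live birth, Section V.A lists treatment, then "clinical sites (if needed), prior exposure to either clomiphene citrate or metformin XR, and other explanatory factors on live birth rate". Prior exposure is therefore unconditional and site is not. The condition is spelled out just before, after a test of interaction at 0.10: "In the event that there is a significant interaction term, clinical site will be included as a covariate in all subsequent secondary analyses". The same paragraph adds: "Sites with similar live birth rates may be collapsed".

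The synopsis puts no condition on site. Its logistic models evaluate "treatment condition, clinical site, prior exposure to either clomiphene citrate or metformin XR, body mass index" and other variables. Section V.C repeats the conditional wording, then lists clinical site again among its example covariates. Its Cox models are given no covariates.

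**The concern.** Blocked randomisation within strata makes the arms more alike on site and prior exposure than simple randomisation would. If those factors predict live birth, the ordinary chi-square uses a variance that is too large for the design. The test then rejects less often than its nominal level and gives up some power. The protocol does expect prior exposure to matter: Section IV.B.1 builds the clomiphene planning rate from 7% in clomiphene-resistant women and 30% in women without prior exposure.

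The rule for site has two faults whatever the size of that loss. An interaction test asks whether the treatment effect varies by site. It does not show whether live birth rates differ by site, which is the reason to adjust. When the interaction is significant, the remedy is a main-effect covariate, which does not address an interaction. Merging sites on observed live birth rate also defines the model's groups from the outcome being modelled, with no threshold given. At stake are a little efficiency in the primary test and a data-dependent form for the exploratory models.

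**Working it through.** **1. The plan's own figure.** Section IV.B.5 gives 45% vs 30%, two-sided alpha 0.025, 80% power and no continuity correction. With pooled variance under the null:

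n = [2.2414 × √(2 × 0.375 × 0.625) + 0.8416 × √(0.45 × 0.55 + 0.30 × 0.70)]² / 0.15² = (1.535 + 0.569)² / 0.0225 ≈ 197 per arm.

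This matches the stated 197, and the other three rows (206, 185, 168) also match. The dropout figure is 197 × 1.15 = 226.55, taken as 226. The design is therefore sized for the unstratified chi-square, with formula power of 0.801 at 197 and 0.857 at 226 per arm.

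**2. How much prior exposure explains.** Section IV.B.1 takes 25% as previously treated. The share of outcome variance explained is 0.25 × 0.75 × gap² / [p(1 − p)].

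- Clomiphene arm, 7% vs 30%: p = 0.2425, and 0.1875 × 0.23² / (0.2425 × 0.7575) = 0.00992 / 0.1837 = 5.4%.
- Combination arm, 36.2% vs 47.6%: p = 0.4475, and 0.1875 × 0.114² / (0.4475 × 0.5525) = 0.00244 / 0.2472 = 1.0%.

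Applied to 197 per arm, that is worth about 2 to 11 women per arm.

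**3. Size of the tests.** An approximate check uses a 23-point gap around a common 30%. The explained share is 0.00992 / 0.21 = 4.7%, so the unstratified statistic has SD √(1 − 0.047) = 0.976 under the null. The critical value 2.2414 acts like 2.2414 / 0.976 ≈ 2.296, a two-sided probability of about 0.0217. Simulation with no site variation gave 0.0216.

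The simulations (100,000 runs for size) used 24 strata, balanced allocation within strata and a fixed two-arm comparison. Nominal alpha was 0.025.

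| Assumed site SD (logit) | Chi-square, no exposure gap | Chi-square, 23-point gap | CMH, both settings |
|---|---|---|---|
| 0 | 0.0257 | 0.0216 | 0.0249–0.0255 |
| 0.25 | 0.0244 | 0.0202 | 0.0241–0.0250 |
| 0.5 | 0.0223 | 0.0188 | 0.0248–0.0250 |
| 0.75 | 0.0187 | 0.0165 | 0.0247–0.0248 |

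The Monte Carlo standard error is √(0.025 × 0.975 / 100,000) ≈ 0.0005.

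**4. Power near the design effect** (50,000 runs per setting, about 45% vs 30%, alpha 0.025). The protocol gives no metformin rates by prior exposure, so gaps of 0, 11.4 and 23 points around 30% were tried. The ranges below span those choices.

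| Assumed site SD | CMH gain at 197 per arm (points) | CMH gain at 226 per arm (points) |
|---|---|---|
| 0 (exposure only) | −0.1 to +1.1 | +0.2 to +1.2 |
| 0.25 | +0.3 to +1.5 | +0.5 to +1.5 |
| 0.5 | +1.4 to +2.6 | +1.4 to +2.2 |
| 0.75 | +3.3 to +4.1 | +2.6 to +3.2 |

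For example, at 226 per arm, SD 0.5 and an 11.4-point gap in both arms, power goes from 86.2% to 87.7%. The standard error of one power figure is about √(0.85 × 0.15 / 50,000) = 0.16 points, so the −0.1 is indistinguishable from zero.

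**5. The site rule.** No arithmetic applies. In Section V.A, site depends on the interaction test. In the synopsis, it is listed outright. In Section V.C, it is conditional in one sentence and an ordinary example covariate in a later one. These cannot all be followed.

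**The case against.** The strongest reply is that nothing in the primary analysis is wrong. The chi-square is a valid test, it is the test the trial was sized for, and its error is on the conservative side. Covariate-adjusted logistic models of live birth are already planned, with prior exposure always in them. The 7% vs 30% contrast belongs to clomiphene alone, and the 7% to resistant women. The combination arm, which is always in the first comparison, has a much smaller gap. A material gain needs site variation that the protocol does not quantify. The site rule touches only analyses declared exploratory, and pooling of small sites is commonly left to the analysis plan, which is not at hand.

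Most of this stands, and it limits the point to a minor one. It does not remove it. The protocol itself fixes the choice of primary test, and Section V.F defers only the critical value to the detailed analysis plan. The interaction gate and the outcome-based merging are also written into the protocol rather than left open. An exploratory label does not make an interaction test informative about whether site predicts outcome.

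**Conclusion.** The point holds as a low-severity efficiency and drafting matter. The primary test ignores both stratification factors and is mildly conservative, with size about 0.017 to 0.026 at nominal 0.025. Stratifying gains about 0 to 1 point of power from prior exposure alone at the design effect and 226 per arm, and about 1.4 to 3.2 points under an assumed site SD of 0.5 to 0.75. These figures also rest on assumed metformin rates by exposure and on a fixed pair of arms; they do not model the choice of the better single agent. The defect in the site rule does not depend on any of these numbers.

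A reader might infer more, and the documents do not support it:

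- **False positives.** The error of the unstratified test runs the other way.
- **A trial short of its stated power.** This point does not show that: 197 per arm reproduces exactly. The conflict between alpha 0.025 in Section IV.B.5 and 0.05 in Section V.A is a separate matter. It moves power at 197 per arm from 0.80 to 0.87, more than stratification does in any setting tried.
- **A larger gain.** Simulation with the 7%/30% gap, site SD 0.5 and a 10-point effect gives 51.4% to 55.7%. But the design difference is 15 points, and that gap is documented only for clomiphene alone.
- **Inflated standard errors in the logistic models.** Adjustment there generally does not shrink the standard error of the log odds ratio; it gains power by moving the estimate away from the null. Prior exposure is already included.
- **A liberal CMH test.** A run of 3,000 trials has a standard error of √(0.025 × 0.975 / 3,000) ≈ 0.003 on size, so a value such as 0.027 would be noise. The larger runs give about 0.025.

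**What to change.** Make a CMH test stratified by site and prior exposure the primary test for both planned comparisons. Pool small sites by a rule fixed before unblinding, and report a stratified risk difference with its confidence interval. Keep the plain chi-square as a sensitivity analysis, which preserves the link to the sample size calculation.

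In the logistic models, which already carry prior exposure, include site without the interaction condition. Include both factors in the GEE and Cox models. Report the site-by-treatment interaction descriptively, and delete the option to merge sites on observed live birth rate. Align the synopsis with Sections V.A and V.C.

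The cost is protocol and analysis-plan wording, settled before unblinding. It needs no extra women, visits or data, because site and prior exposure are already recorded for randomisation.

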c) The null hypothesis is accepted, but no statistically significant differences are observed between any of the treatments.

If the observed differences between all three agents are less than 15%, then the choice of initial treatment will likely be based on side effects, convenience, costs, etc.

Although this trial will not be able to definitively answer that issue, data collected from this study will allow planning of additional studies to address issues of cost-effectiveness, health-related quality of life, patient preferences, etc.

NICHD Reproductive Medicine Network
PPCOS-Pregnancy in Polycystic Ovary Syndrome Protocol
Given these considerations, at most two comparisons are needed

- Scenario 1: Point estimate of live birth rate with combination therapy higher than with either agent alone

Comparisons: (1) Combination therapy vs. highest single agent, (2) single agents to each other.

Rationale: In order to be preferred, combination therapy needs to be superior to both agents. If combination is not superior to the agent with the highest live birth rate, demonstration of superiority to the other agent is not clinically meaningful. Direct comparison of single agents becomes the critical comparison for decision making.

- Scenario 2: Combination therapy less effective than one of the single agents

Comparisons: 1

Rationale: Given cost, complexity, side effects, etc., combination therapy must be demonstrably more effective than single agent therapy in order to be clinically preferable. In this scenario, only the comparison between the two single agents is meaningful.

5. Sample Size Calculations

Primary Endpoint - Live Birth Rate

Assumptions

- 15% absolute difference considered to be clinically meaningful
- 15% dropout rate
- Overall alpha level = 0.05, two-tailed test
- Two planned comparisons

NICHD Reproductive Medicine Network
 PPCOS-Pregnancy in Polycystic Ovary Syndrome Protocol

1) Lowest rate vs. second lowest rate

2) Second lowest rate vs. highest rate

- χ^2 test for differences in proportions
- Best estimated live birth rates:
 - 1) Metformin alone: **30%**
 - 2) Clomiphene alone: **25%**
 - 3) Metformin + clomiphene citrate: **45%**

Parameters for sample size calculations:

- Alpha = **0.025**, two-tailed tests since two planned comparisons
- Beta = **0.20**, or 80% power

Sample Size

Treatment 1 (live birth rate)	Treatment 2 (live birth rate)	Required Sample Size	Sample Size with dropout adjustment	Total Sample Size

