- An ovulation will be defined as an elevated weekly progesterone level separated by at least one week with a nonovulatory progesterone level. A binary variable indication whether the patient ovulated or not will be created for each cycle. Furthermore, cycles to first ovulation will be used as time to event variable.
- Time to pregnancy is defined as the number of cycles required to achieve a viable implantation (detection of fetal heart beat). Weeks from pregnancy to live birth will also be used as a time to event variable for patients who did not have miscarriages.
- Conception. Conception is confirmed by a positive serum hCG value. Cycles to first conception will be used as a time to event variable.

E. Drop outs/Treatment Failures

Dropouts, either by patient choice or physician recommendation due to adverse effects or poor compliance will be analyzed by intention to treat as treatment failures. Subjects who have completed 30 weeks or 6 treatment cycles without a pregnancy will also be considered as treatment failures. Subjects who conceive and are lost to follow up will be considered as a treatment success. It is considered unlikely that the patients will be lost to follow-up after a conception on a treatment regimen.

NICHD Reproductive Medicine Network
PPCOS-Pregnancy in Polycystic Ovary Syndrome Protocol

F. Interim Analysis

Analysis Plan: An interim analysis will be conducted on the primary endpoint when 50% of the study participants have completed treatment. The primary analysis described above will be performed and the O'Brien-Fleming (1979) method will be applied to adjust for at the number of looks at the primary endpoint. The interim analysis should also provide a detailed summary of adverse events reported. The critical value for the primary analysis will be specified in the detailed analysis plan. The results of the interim analysis will be submitted to the Data Safety and Monitoring Committee (DSMC). The interim analysis results will be presented in a blinded fashion to the DSMC, who will then evaluate the findings to determine whether the trial should be continued, modified, or discontinued.

Stopping Rules: The stopping rule for the O'Brien-Fleming method compares the statistic Z_i with $Z^*(N/i)^{.5}$, where Z^* is the critical value for the significance level (.05), N is the total number of analyses ($N = 2$) and i is the analysis number (for the one planned analysis, $i = 1$).

VI. DISCLOSURE OF DATA

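### The trial is sized at two-sided 0.025 per primary comparison, but the analysis section tests both comparisons at 0.05, and the testing sequence does not protect the stated overall 0.05

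*Protocol*

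**What the plan says.** **Design.** Protocol IV.B.5 lists "Overall alpha level = 0.05, two-tailed test" and "Two planned comparisons" among its assumptions. Its parameter list then gives alpha as 0.025, with the reason "two-tailed tests since two planned comparisons".

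**Analysis.** The opening of section V says "The level of significance will be set at 0.05 for primary analyses and 0.05 for secondary analysis" and "All statistical tests will test non-directional hypotheses". Section V.A compares the combination with whichever single agent has the higher observed live birth rate, and then continues: "If the test is not significant, a standard chi-square test will be used to examine differences in proportions in live births" between the two single agents. It closes with "The level of significance for all tests included in the primary analysis will be 0.05". The synopsis describes the same sequence.

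**Interim.** The stopping rule in V.F takes Z* at the .05 level. The same section names the O'Brien-Fleming method and leaves the critical value to the detailed analysis plan.

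**Decision logic.** Section IV.B.4 names the combination as treatment of choice if the first null hypothesis is rejected. It names a single agent if the first is accepted and the second rejected. Its Scenario 2 says that when the combination falls below one single agent there is one comparison, that of the two single agents. Section V.A does not repeat this rule.

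**The concern.** The same two tests are given two significance levels, and nothing in the protocol reconciles them. The order of testing does not justify a full 0.05 for each. A fixed sequence keeps the overall error at 0.05 when the second hypothesis is tested only after the first has been rejected. Here the second is tested only after the first has failed, so its error adds to that of the first.

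The primary conclusion is at stake. If the first or second comparison gives p = 0.03, section V declares a difference and the design section does not. That choice should not be open once data are available. An analysis plan cannot settle it quietly, because using 0.025 would contradict section V and using 0.05 would contradict IV.B.5.

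**Working it through.** **1. Which alpha sized the trial.** Inputs from IV.B.5: 45% v 30%, 80% power, two-sided, chi-square without continuity correction.

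n per arm = [z(1−α/2)·√(2·p̄·q̄) + z(0.80)·√(p1q1 + p2q2)]² / (p1 − p2)²

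with p̄ = 0.375, √(2 × 0.375 × 0.625) = 0.6847, √(0.2475 + 0.2100) = 0.6764, z(0.80) = 0.8416.

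- α = 0.025: (2.2414 × 0.6847 + 0.8416 × 0.6764)² / 0.0225 = 196.7, so 197.
- α = 0.05: (1.9600 × 0.6847 + 0.8416 × 0.6764)² / 0.0225 = 162.3, so 163.

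| Rates | Protocol | α = 0.025 | α = 0.05 |
|---|---|---|---|
| 50% v 35% | 206 | 206 | 170 |
| 45% v 30% | 197 | 197 | 163 |
| 40% v 25% | 185 | 185 | 152 |
| 35% v 20% | 168 | 168 | 138 |

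All four rows match 0.025 and none matches 0.05.

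**2. Error of the sequence.** Each setting was simulated with 2,000,000 trials: 226 per arm (IV.C), equal true rates in all arms, pooled chi-square, one look. The first test is the combination against the single agent with the higher observed rate. The second is single agent against single agent, if the first is not significant. Equal rates are an assumption, varied from 15% to 45%.

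At a rate of 30% with both tests at 0.05:

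- first test rejects, combination worse: 4.5%
- first test rejects, combination better: 0.4%
- second test rejects after a non-significant first: 4.1%
- any rejection: 9.1% from the unrounded parts

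Two independent tests would give 1 − 0.95² = 9.75%. The 'combination worse' share is large because the comparator is chosen as the higher observed rate.

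**3. By reading of the rule, rate 30% (range over 15% to 45%).**

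| What is counted | Both at 0.05 | Both at 0.025 |
|---|---|---|
| Section V as written, any rejection | 9.1% (9.1–9.5) | 4.7% (4.6–4.9) |
| Scenario 2 applied: first test skipped if combination is below a single agent | 5.5% (5.5–5.8) | 2.7% (2.6–2.8) |
| Combination superior, or single-agent difference after a non-significant first test | 4.6% (4.6–4.7) | 2.4% (2.3–2.4) |

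**4. Power at 0.025 for 45% v 30%.** 80.1% at 197 per arm, so the stated 80% already rests on this level.

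**The case against.** A reader might infer that the trial simply runs at 9% instead of 5%, or that a declared treatment of choice carries a 9% error. The document does not support either without qualification.

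- About half of the 9.1% is the combination being found worse than the better single agent. Section V counts this because its tests are non-directional, but IV.B.4 reads rejection of the first null as combination superiority. Falsely reaching an outcome to which IV.B.4 attaches a treatment of choice has a probability of about 4.6% even at 0.05 per test. This counts a single-agent difference in either direction and does not impose the 15-point observed difference also mentioned there.
- Scenario 2 in IV.B.4 would drop the first test in just the cases that produce those rejections, which leaves about 5.5%.
- The 9.1% needs all three rates to be equal. If the combination is truly better than two equal single agents, only the second test can err.

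These objections stand, and they limit the size. They do not remove the contradiction, because section V neither repeats Scenario 2 nor restricts direction, and IV.B.5 still promises 0.025 per test.

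A reader might also infer further inflation from the interim look by taking Z* as 1.96. That does not follow. V.F names O'Brien-Fleming and defers the critical value to the analysis plan, so the constant is not fixed here. Only the 0.05 level is.

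**Conclusion.** The inconsistency is real and concerns the primary conclusion. The sample sizes reproduce only at 0.025 per comparison, while V, V.A and V.F state 0.05, and testing the second hypothesis after a failed first one gives no protection. The resulting error depends on which section governs: about 9.1% for section V taken literally, about 5.5% under Scenario 2, and about 4.6% for false treatment-of-choice outcomes. These figures assume equal rates in all arms, 226 per arm and no interim look. What does not depend on the reading is that p-values between 0.025 and 0.05 lead to opposite conclusions under the two sections.

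**What to change.** In the opening of V, in V.A and in V.F, state two-sided 0.025 for each of the two primary comparisons, as used in IV.B.5. Apply the O'Brien-Fleming boundary at that level within each comparison, with the critical value given in the detailed analysis plan as V.F already provides. In V.A, say whether Scenario 2 of IV.B.4 applies, so that the testing sequence and the alpha agree.

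This is a change of wording only. It holds the error at about 4.7% under the literal rule and loses nothing against the stated 80% power. If Scenario 2 is adopted, 0.025 per test is conservative (about 2.7%), so the sequence should be settled together with the level, before unblinding.

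### Exploratory site analyses allow sites to be merged on their observed live-birth rates, which makes any site effect tested on the merged groups circular and can weaken the site-by-treatment test

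*Protocol*

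**What the plan says.** Protocol V.A, under Supplemental analyses, sets out a sequence:

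1. "Initially, a comparison of the internal consistency of live birth rates across sites will be examined using logistic regression analysis".
2. "Sites with similar live birth rates may be collapsed".
3. "For the regression model, the data will be examined to determine whether there is a site by treatment interaction effect". On its level: "The recommended significance level is an alpha of 0.10 since the power to detect interactions is low".
4. "In the event that there is a significant interaction term, clinical site will be included as a covariate in all subsequent secondary analyses".
5. Logistic models then assess how well treatment, site (where needed), prior drug exposure and other factors predict live birth.

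V.C carries the same conditional use of site into the models for the secondary efficacy measures. Site is also a randomisation factor (IV.C.2.a): "Stratification variables will be site and prior exposure to either" of the two study drugs. The status of the supplemental work is stated plainly: "All secondary analyses of the primary endpoint will be considered exploratory since the study has not been adequately powered" for it. The primary chi-square comparison in V.A contains no site term.

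**The concern.** The criterion for merging is the outcome. Two problems follow.

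First, groups formed because their members had similar observed live-birth rates differ in live birth by construction. If the grouping is then offered as an explanatory factor for live birth, its test no longer has its nominal level.

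Second, two sites can share an overall rate and have quite different treatment effects. Merging them averages those effects before the interaction test looks for the difference. The plan acknowledges that this test has low power and relaxes its level to 0.10 for that reason, so a preceding step that removes power works against the plan's own intention.

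At stake are the statement on whether site predicts live birth, and the check of consistency across centres that decides whether site enters the later secondary models.

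**Working it through.** **Inputs from the Protocol.** 12 centres (IV.N); 678 women, 226 per arm (IV.B.6); assumed live-birth rates of 30% metformin, 25% clomiphene and 45% combination (IV.B.5); interaction level 0.10 and secondary level 0.05 (V.A). With equal sites, 678/12 = 56.5 women per site and 226/12 = 18.8 per site and arm, taken as 19 (57 per site).

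**The plan's own figures.** It gives none for the site analysis. Its rates do reproduce its sample size. With p̄ = 0.375, two-sided alpha 0.025 and 80% power, n = [2.241·√(2·0.375·0.625) + 0.842·√(0.45·0.55 + 0.30·0.70)]² / 0.15² = 196.7, which rounds up to the stated 197 per arm.

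**Assumptions.** The plan gives no number of groups and no margin for similarity, so several were tried: 2, 3, 4 or 6 groups of sites ranked on observed rate, and merging sites within 5 or 10 points. Tests are likelihood-ratio tests in logistic models, with 500 to 1,500 simulated trials per scenario.

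**Hand check of the circularity.** The mean rate is (30 + 25 + 45)/3 = 33.3%. By chance alone a site's observed rate has SD √(0.333·0.667/57) = 6.2 points. Rank 12 equal sites and form three groups of four. The mean expected normal score is about 1.02 in the top group and −1.02 in the bottom group, so the expected gap is 2·1.02·6.2 ≈ 12.7 points. A comparison of two groups of 4·57 = 228 women takes the standard error to be √(2·0.333·0.667/228) = 4.4 points. The gap is then about 2.9 standard errors with no true difference.

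**Site effect, no true site difference, tested at 0.05**

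| Sites used | False positives |
|---|---|
| 12 sites | 5.3% |
| 2 / 3 / 4 / 6 outcome-sorted groups | 86 / 76 / 65 / 40% |
| Merge within 5 / 10 points | 74 / 87% |
| 3 groups merged at random | 4.2% |

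Repeat runs gave 75% for three sorted groups and about 6% for the 12 sites. The random-merge row shows that the outcome criterion is the cause.

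**With the interaction gate.** If site is tested only after a significant interaction, and no interaction exists, the merged interaction test opens the gate about 10.5% of the time. Then 0.105 × 0.76 ≈ 0.08. Direct simulation gave 7 to 8%.

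**Interaction power at 0.10**

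| Scenario (assumed) | 12 sites | 2 / 3 / 4 / 6 sorted groups | 5 / 10-point merge | 3 random groups |
|---|---|---|---|---|
| Site-specific treatment log-odds SD 0.5, unrelated to site rate | 85% | 35 / 42 / 49 / 65% | 50 / 36% | 38% |
| Combination and clomiphene rates swapped in half the sites | 90% | 29 / 42 / 49 / 62% | 47 / 34% | 42% |
| Effect rises with site rate, site SD 0.5 | 68% | 68 to 71% | not run | 27% |
| Effect rises with site rate, site SD 0.3 | 39% | 33 to 36% | not run | 19% |

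A repeat run of the swapped scenario gave 87% with 12 sites and 38% with three sorted groups. With no true interaction the merged tests reject in 9.5 to 11%, so their size is kept. The 12-site likelihood-ratio test rejects in 14% because cells are sparse, so its power is somewhat overstated. The gap in the first two rows is far larger than that.

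**Treatment estimates.** The combination-versus-metformin log odds ratio averaged 0.655 (SE 0.197) unadjusted and 0.665 (SE 0.199) adjusted for outcome-sorted groups. Type I error for treatment was 5.0% and 5.1%.

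**The case against.** The strongest reply is that 75% is not the plan's error rate. The text only permits merging, places it after a consistency check, and lets site into later models after a significant interaction or where needed. With that gate and no true interaction, the false site finding is about 7 to 8%. If a non-significant consistency check led to pooling all sites (an assumed reading), it would be about 4%. This stands: the large figure applies only when merging is done and site is then tested without the gate.

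A reader might infer that merging on outcome always hides an interaction. The results do not support that. Power is largely kept when the treatment effect tracks the site rate, and where it is lost, random merging loses about as much. The loss comes from merging at all, and only the false site effect is specific to merging on outcome.

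A reader might also infer that the trial's main result, or the treatment effects in the secondary models, are compromised. They are not: the primary test has no site term, randomisation is stratified by site, and the estimates above hardly move.

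Finally, V.F foresees a detailed analysis plan, which could define similarity or never use the option. That is fair as to thresholds. But the protocol itself names the criterion, and a threshold on observed live-birth rates would still group sites on the outcome.

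**Conclusion.** The point holds in a limited form. The protocol states a faulty permissive rule in an exploratory section. If it is used:

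- A site effect tested directly on the merged groups is circular. With three sorted groups there are about 75% false positives, against 5 to 6% with the 12 sites. The range over the other rules tried is 40 to 87%, and behind the interaction gate, with no true interaction, it is about 7 to 8%.
- Interaction power can fall substantially, for example from 87–90% to 38–42% with swapped effects and three groups, or hardly at all when effects follow the site rate.

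These sizes rest on equal sites, the plan's 30/25/45% rates, and assumed grouping rules and patterns of heterogeneity. The primary analysis is unaffected. The change is worth making because it is nearly free and removes a rule that gives a wrong answer when followed.

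**What to change.** In V.A, delete "Sites with similar live birth rates may be collapsed". Test site by treatment with the 12 sites as randomised, preferably with a random site-by-treatment effect, which also deals with sparse cells. Where a site is too small to fit, pool it by an enrolment threshold fixed in advance without outcome data.

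Testing the interaction on two broad outcome-free groups, such as the eight network centres against the four SCCPRR centres, is not a substitute. With swapped effects unrelated to the network, an 8-versus-4 split has about 29 to 30% power, no better than merging on outcome.

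The cost is a sentence or two of text, plus more site terms or a mixed model. Sample size, conduct and the primary test do not change.
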